As shown in Table 3 on the next page, we have planned a comprehensive evaluation of both process and clinical outcomes to fulfill our second objective. Clinical outcomes will include four patient-centered outcomes, and process outcomes will include five measures of adherence to the CP (e.g., physician provision of discharge instructions; patient/parent adherence to key interventions as recommended by the CP). Physicians and nurses in the ED will distribute a concussion handout at discharge. The front page will advise the family to go to the RECOVER web portal for more information, and the last 4 pages will provide concussion education and advice, including about return to learn and return to play. Prior to CP implementation, the website will provide parents with tools to help track recovery; after CP implementation, it will also supply evidence-based information about how to promote recovery and obtain appropriate concussion care. Both prior to and after CP implementation, the website interface will ask patients and parents to rate their satisfaction with their care in the ED within 3 days of their visit, as well as their comprehension of and adherence to physician discharge recommendations, including those regarding return to school and return to play. They also will report on whether they perceive the patient to have returned to pre-injury status, and provide ratings of the patient's post-concussive symptoms and quality of life. Parents and patients will be blinded to site allocation. They will be able to provide their responses anonymously, or they can elect to provide informed consent to enable us to link their responses on the website to identifying information and medical data.

12b The primary outcome will be the time to symptom resolution based on weekly reports of whether the patient has returned to pre-injury status. Secondary patient-centered outcomes will include ratings of satisfaction with ED care and post-injury ratings of post-concussive symptoms and quality of life. The latter two outcomes will be assessed using the Health and Behaviour Inventory and the PedsQL, both of which are measures included in the NIH Common Data Elements for pediatric traumatic brain injury (see Surveys and Questionnaires in appendices).

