12d *Health care utilization.* We will assess the impact of the implementation of the CP on health care utilization using data from the National Ambulatory Care Reporting System (NACRS). Relevant outcomes will include acute care length of stay and return visits within 72 hours following acute care discharge. Appropriate procedures will be used to link administrative and health data. Use of NACRS data allows efficient capture of return visits, regardless of whether the patient returns to the index site. We will also use administrative data from AHS to assess health care utilization for pediatric patients with concussion. For each concussion diagnosed at the target sites, we will track the duration of stay in the ED, number of subsequent outpatient visits, and number of referrals to other health care services.

*Healthcare costs.* Payer costs associated with acute care for pediatric patients with concussion will be accounted for, based on ED visits, return visits, and physician fees, as well as subsequent outpatient care, which will be determined from the AHS administrative database. Costs for ED visits will be based on standard methodologies using resource intensity weightings (RIWs). Physician fees associated with ED and outpatient visits, including those for laboratory and diagnostic imaging services, will be captured through associated AHS billings. Cost data will be presented in Canadian dollars for the standard price year of 2014.

Participant timeline 13a *Project phases.* As shown in the Project Timeline below, the project will be divided into four phases. During the pre-implementation phase, which will last 12 months, we will complete site visits and key informant interviews, develop the intervention strategy, seek site approvals for the planned intervention, conduct a launch meeting, and complete randomization. The implementation phase will take place over the next 10 months. According to the stepped wedge design, data collection will occur continuously from 2 months prior to implementation at any site until 2 months after the CP is implemented at all four sites. Data collection will include the monitoring of outcomes, which are described below, during the course of the stepped wedge trial, which will last about 10 months.

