*Power calculation.* Power calculations for the primary outcome, time to symptom resolution, were computed using standard methods for two-group survival analyses (i.e., children who received care before versus after implementation of the CP). We conservatively assumed a sample size of 1,575, based on a total of 2,100 concussions per year across sites, a 50% rate of web site usage, and 18 months of recruitment. If we assume equal numbers of cases in the pre- and post-implementation phases, a median time to symptom resolution of 4 weeks, non-informative censoring because follow up will continue for 3 months, and no clustering effects, then the minimum hazard ratio that we can detect with .80 power at a significance level of .05 would be 1.20, which would represent at 20% higher likelihood of symptom resolution at any given time post-injury after implementation of the CP. Analyses will treat the randomised crossover from control to intervention as having occurred at the planned time, irrespective of any delays in actual implementation of the intervention, although secondary analyses will explore the effects of the actual timing of the crossover should any delays occur. All sites have provided written commitment to the study. Therefore, barring exceptional circumstances, no sites will be lost to follow-up.

Randomization

15

A study statistician will use a computerized algorithm to select a randomly generated order of implementation for the four sites.

Recruitment 16 Recruitment will rely on ongoing support and communication with clinicians. To avoid having implementation become stalled or displaced by other priorities, we will conduct monthly teleconferences with site champions to discuss progress and sustainability. Teleconferences will allow sites to discuss best practices and local solutions to common barriers. Additionally, the study coordinator and PI will be available for more informal consultation by email or phone.

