17b The web portal will send email reminders to participating families to complete serial symptom inventories. No contact will be made by the study team unless families reach out voluntarily. Ideally, symptom data will be collected until participants fully recover, however, participants can stop entering data, or leave the study at any time.

Data management 18 The study team will not directly access AHS databases or systems. Administrative data will be accessed externally by an AHS MyChild analyst. The variables collected will be obtained for all children diagnosed with concussion at any of the participating AHS facilities during the conduct of the stepped wedge clinical trial. The data will be de-identified, except for children whose parents have consented to linkage of web portal responses with health records. Individual data entered through the web portal by parents and children will download into the secure REDCap database. The database servers will be located under Canadian jurisdiction and be administered by the Clinical Research Unit of the University of Calgary. These servers are part of the CRU infrastructure and maintained in accordance with strict security and privacy controls.

Results from the project will be reported in aggregate format. If individual materials are presented, all personal identifiers will be removed. These safeguards should maintain confidentiality and minimize any risks associated with participation in the project.

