Statistical methods 19a Statistical analyses will involve comparisons of primary and secondary outcomes prior to versus after CP implementation. Children will fall into either the pre-CP or post-CP group because their care (including the version of the website and text messaging they receive) will be based strictly on when they present for acute care (i.e., prior to or after CP implementation at their respective site). Time to symptom resolution will be the primary outcome, and will be examined using survival analyses. First, Kaplan Meier estimates of the curves will be created, to obtain crude comparisons; Cox proportional hazards models will then be used to adjust for other variables. Apart from reporting hazard ratios, we also will present median time to symptom resolution (if reached) for pre- versus post-CP implementation. Other outcomes will be examined using mixed models with random effects for cluster, to adjust for clustering by site, and fixed effects for the test of CP status (pre/post implementation). Linear models will be used for continuous outcomes, Poisson for counts, and logistic regression models for binary outcomes. Exploratory analyses will examine whether the impact of implementation changes as sites gain more experience with the CP, by including the amount of time since the CP was implemented as a fixed effect in the model. Similarly, heterogeneity in intervention effects will be explored using testing interactions of CP status (pre/post) with site.

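### Three months of follow-up does not make drop-out from weekly portal reporting non-informative, and the stated data-collection window leaves late children short of those 3 months

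*Protocol*

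**What the plan says.** Item 14 (Sample size, Power calculation) derives the detectable HR for the primary outcome under a list of conditions: equal groups, a 4-week median, no clustering, and "non-informative censoring because follow up will continue for 3 months". The only loss it goes on to discuss is the loss of whole sites.

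The primary event exists only if a family reports it. Item 12b defines time to symptom resolution "based on weekly reports of whether the patient has returned to pre-injury status". Item 17b says: "Ideally, symptom data will be collected until participants fully recover". It adds that "participants can stop entering data, or leave the study at any time". Prompts are automatic: "The web portal will send email reminders to participating families to complete serial symptom inventories". The study team does not contact families unless they make the first approach.

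Item 19a plans Kaplan-Meier curves, after which "Cox proportional hazards models will then be used to adjust for other variables". It also promises a summary: "we also will present median time to symptom resolution (if reached) for pre- versus post-CP implementation". Items 12a and 19a make clear that the website a family sees differs by period: tracking tools before the CP, tracking tools plus recovery information after it.

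On timing, item 13a has data collected "until 2 months after the CP is implemented at all four sites" and places outcome monitoring inside a trial of about 10 months. The Overview of the design gives the same end point.

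**The concern.** There are two separate problems.

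**A. The reason does not support the assumption.** A fixed 3-month cut-off is non-informative censoring by design. A family that stops logging in is another matter. If a child recovers and the family then loses interest without recording it, the planned Kaplan-Meier and Cox analyses censor that child at the moment of the event. Follow-up of any length does not cure this. If it happens more often in one period than in the other, the primary HR is shifted, in either direction. The portal, which is the measuring instrument, changes content at crossover, so equal loss cannot simply be presumed.

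**B. The window is too short for the follow-up it should contain.** If outcome monitoring ends 2 months after the last crossover, no child seen after that crossover can have the 3 months that item 14 assumes, and some seen earlier cannot either.

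**Working it through.** **The plan's own figure.** N = 2,100 × 0.50 × 18/12 = 1,575, which agrees with item 14. For the HR, take exponential recovery with λ = ln2/4 per week and 3 months = 13.04 weeks. Event shares are 1 − 0.5^(13.04/4) = 0.896 before the CP and 1 − 0.5^(1.2 × 13.04/4) = 0.934 after it at HR 1.20, so there are about 787.5 × (0.896 + 0.934) ≈ 1,440 events. The detectable HR (two-sided 0.05, power 0.80, 1:1) is exp[2 × (1.960 + 0.842)/√1,440] ≈ 1.16, and power at HR 1.20 is about 0.93. The stated 1.20 is therefore not reproduced. It lies on the cautious side of its own inputs, and nothing below depends on that gap.

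**Part A.** Suppose a share p of families stop exactly at recovery without logging it. The hazard of a reported recovery is then (1 − p)λ, so

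- observed HR = true HR × (1 − p_post)/(1 − p_pre)
- observed median = 4/(1 − p) weeks

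The protocol gives no rates. Those below are assumptions for illustration, with a true HR of 1.00.

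| Unreported pre / post | Calculation | Observed HR |
|---|---|---|
| 30% / 20% | 0.80/0.70 | 1.14 |
| 25% / 20% | 0.80/0.75 | 1.07 |
| 30% / 30% | 0.70/0.70 | 1.00 |
| 20% / 25% | 0.75/0.80 | 0.94 |
| 20% / 30% | 0.70/0.80 | 0.88 |

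A two-group Cox simulation of the 30%/20%, 20%/30% and 30%/30% rows gave 1.145, 0.873 and 0.999. Equal loss of 10%, 20% or 30% leaves the HR alone but makes a 4-week median read as 4.4, 5.0 or 5.7 weeks.

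The mechanism is decisive. When the same unreported shares arise from stopping that is independent of recovery, simulation gives an HR of 1.00 and a median of 4.0 weeks. Such stopping costs only events: at N = 1,575, with 20%, 40% or 60% of families stopping by 13 weeks, power at HR 1.20 is 0.92, 0.89 or 0.86.

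**Part B.** Assume four equal sites, uniform accrual, crossovers at months 2, 4, 6 and 8 (Overview) and closure at month 10 (item 13a). Each period has 20 site-months: 8 + 6 + 4 + 2 post-CP and 2 + 4 + 6 + 8 pre-CP. Children seen in months 7 to 10 cannot reach 3 months:

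- post-CP: (3 + 3 + 3 + 2)/20 = 11/20 = 55%
- pre-CP: 1/20 = 5%

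Events lost are 9.1% at HR 1.20 and 9.8% at HR 1.00. At N = 1,575 and HR 1.20, events fall from about 1,441 to 1,309 and power from 0.93 to 0.91. The Cox HR under this truncation alone stays at 1.002 (true 1.00) and 1.202 (true 1.20). If the 11 months named in the Overview put the extra month at the end (an assumption), 50% of post-CP and no pre-CP children are cut short, and 8.3% to 8.9% of events are lost.

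**The case against.** Item 14 does not assert that drop-out is harmless. It lists non-informative censoring among the conditions of a power calculation, and 3 months has a sensible role there: with a 4-week median, about 90% of recoveries fall inside it. The protocol already asks the recovery question weekly and sends reminders. Drop-out tables and sensitivity analyses commonly sit in the SAP. On timing, item 13a may describe only the stepped-wedge window, and the item 13b chart spreads data collection over three half-year columns, which leaves room for a tail.

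Much of this stands. Non-informative censoring may remain as an assumption, and removing the stated reason would on its own be editorial. The chart is not a further contradiction, although no section states a tail. What does not stand is leaving everything to the SAP. A sensitivity analysis cannot restore recovery dates that were never obtained, and item 17a says account details are not kept by the study team, so approaching families later is largely closed off.

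A reader might infer two stronger things. One is that the primary HR is biased. The documents do not support that: they give no rates, no mechanism and no evidence of a difference between periods, and the distortion arises only if stopping happens at recovery and at unequal rates. The other is that truncation leaves the trial underpowered. With 10 months of accrual, N = 2,100 × 0.50 × 10/12 = 875 and power goes from 0.73 to 0.69 (about 800 to 727 events, against 945 needed for 0.80). Most of that shortfall comes from the separate mismatch between 10 and 18 months of recruitment: 0.93 to 0.73 is the smaller N, and only 0.73 to 0.69 is truncation.

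**Conclusion.** Both parts hold in limited form, and the change should be made.

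**Part A** is an unsupported justification and an unguarded risk, not a demonstrated bias. If families stop at recovery without logging it, a difference of 10 percentage points between periods moves the HR to about 1.14 or 0.88, which is not small beside a target of 1.20. Equal loss of 20% lengthens the reported median from 4 to 5 weeks. If stopping is unrelated to recovery, neither the HR nor the median is affected.

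**Part B** rests on the literal wording of the Overview and item 13a, equal sites and uniform accrual. It costs about 9% to 10% of events, nearly all post-CP, and does not bias the HR. At the stated N the loss of power is about 0.02, under item 14's own assumption of no clustering.

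**What to change.** 1. **Item 13a:** state that enrolment ends 2 months after the last crossover and that portal outcome entry stays open until the last enrolled child reaches 3 months. Reconcile the Overview and item 14 with this.
2. **Item 17b:** add two messages to the existing automated emails, one after missed weekly reports and one at 3 months. Each asks whether the child is back to pre-injury status and, if so, since what date. Wording and schedule must be identical before and after the CP.
3. **Item 14:** keep non-informative censoring as an assumption, but do not present it as a consequence of 3-month follow-up.

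Drop-out by CP status and a sensitivity analysis can be left to the SAP.

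If the messages recovered half of the unreported dates in both periods (an assumption), the 30%/20% case would shrink from 1.14 to 0.90/0.85 = 1.06, and the 20%/30% case would move from 0.88 to 0.85/0.90 = 0.94.

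The cost is two automated messages, up to 3 more months of portal operation with data lock later by as much, and an ethics amendment. No staff contact or extra patients are needed. Recalled dates will carry some error, and emails will not reach families who use the portal anonymously.

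### The stated minimum detectable hazard ratio of 1.20 does not follow from the printed inputs, which give about 1.16; the assumption behind 1.20 is not stated

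*Protocol*

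**What the plan says.** The calculation is in the Power calculation paragraph of item 14 (Sample size). It uses standard methods for a two-group survival comparison of children seen before and after implementation.

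- Sample size: "We conservatively assumed a sample size of 1,575, based on a total of 2,100 concussions per year across sites", with "a 50% rate of web site usage, and 18 months of recruitment".
- Allocation: "equal numbers of cases in the pre- and post-implementation phases".
- Event rate: "a median time to symptom resolution of 4 weeks".
- Follow-up: "non-informative censoring because follow up will continue for 3 months".
- Clustering: "no clustering effects".
- Result: "the minimum hazard ratio that we can detect with .80 power at a significance level of .05 would be 1.20".

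The paragraph gives no expected number of events, no loss or drop-out rate, no distribution of censoring times, and no statement of whether the test is one- or two-sided.

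**The concern.** A survival comparison gets its power from the number of events. With a 4-week median and 3 months of follow-up, about nine children in ten should have an observed resolution. From 1,575 children that is far more events than a hazard ratio of 1.20 requires, so the sample size and the effect size do not match on the printed assumptions.

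This paragraph is the protocol's only justification of the trial's size. Any later adjustment has to start from a known number of events, whether for families who stop reporting (item 17b allows this), for clustering by site, or for a trial shorter than 18 months (item 13a gives about 10). A reader who takes 80% power at 1.20 as the result for complete follow-up starts from the wrong base. If an allowance for loss is already built in without being stated, that reader will subtract it twice.

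**Working it through.** **Inputs from item 14.** N = 1,575; 1:1 split; median 4 weeks; follow-up 3 months, taken as T = 12 and T = 13 weeks; no clustering; power .80; level .05.

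**Assumptions added.** Exponential times, the 4-week median in the pre-implementation group, a two-sided test, and every child followed to T.

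**Step 1: the sample size.** 2,100 × 0.50 × 1.5 years = 1,575. This reproduces.

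**Step 2: events needed for HR 1.20.**
- Schoenfeld: 4 × (1.960 + 0.842)² / (ln 1.20)² = 4 × 7.849 / 0.1823² ≈ 945.
- Freedman: 7.849 × (2.20 / 0.20)² ≈ 950.
- As a share of 1,575: 945 / 1,575 = 60.0%; 950 / 1,575 = 60.3%.

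**Step 3: events expected from the printed inputs.** The proportion resolved by T is 1 − 2^(−T/4) before implementation and 1 − 2^(−1.2T/4) after.

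| | T = 12 weeks | T = 13 weeks |
|---|---|---|
| Resolved, pre | 87.5% | 89.5% |
| Resolved, post (HR 1.20) | 91.8% | 93.3% |
| Events from 1,575 | 1,412 | 1,439 |
| Power at HR 1.20 | 92.9% | 93.3% |
| Minimum HR at 80% power | 1.161 | 1.159 |

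Power is Φ(½ × √events × ln 1.20 − 1.960). For T = 12 this is Φ(3.425 − 1.960) = Φ(1.465) ≈ 0.929. The minimum hazard ratio solves the same expression for 80% power. The stated 1.20 is not reproduced.

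**Step 4: other conventions, keeping the printed inputs.** Freedman gives 1.160 to 1.162, Lachin-Foulkes 1.153 to 1.160, no censoring at all 1.152, and one-sided testing 1.140 to 1.142. A log-rank simulation with 1,575 children gave 93% power at 1.20 and 81% at 1.16. None of these reaches 1.20.

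**Step 5: what would give 1.20.** About 945 to 950 events are needed, and more than one route leads there.
- *Early censoring.* If censoring is spread uniformly over the 3 months, the proportion with an observed event is 1 − (1 − e^(−λT)) / (λT), with λ = ln 2 / 4 pre and 1.2 times that post. For T = 12 this is 57.9% and 63.2%, giving 954 events from 1,575 and a minimum HR of 1.199. For T = 13 it gives 990 events and 1.195.
- *Loss of a fixed fraction of children.* 1 − 945 / 1,412 = 33% for T = 12, and 1 − 945 / 1,439 = 34% for T = 13.
- *Smaller N with complete follow-up.* 945 / 0.896 ≈ 1,054 for T = 12 and 945 / 0.914 ≈ 1,034 for T = 13. At N = 1,050 the minimum HR is 1.200 and 1.198.

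**The case against.** The best defence is that the paragraph does invoke non-informative censoring, and item 17b lets families stop entering data at any time, so some censoring before 3 months is foreseeable. If that censoring were uniform over the window, 1,575 children would give 1.20 by a standard method (Step 5). The arithmetic is right, and it rules out any claim that 1.20 cannot be obtained from 1,575. It does not rescue the figure as printed. It needs about 37 to 39% of children to be censored before resolution (1 − 990/1,575 and 1 − 954/1,575). The paragraph states no such allowance, and it justifies its censoring assumption by saying that follow-up continues for 3 months.

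Two stronger readings are tempting and should be resisted.

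- A reader might infer that 1.20 was computed for 12 months of recruitment, since 2,100 × 0.50 = 1,050, and then printed beside the 18-month sample. The match is close, but the protocol nowhere mentions a 12-month sample or 1,050 children. The match also fails under uniform censoring, where 1,050 children give 1.24 to 1.25.
- A reader might infer that the trial really has 93% power at 1.20. That figure holds only with complete reporting and no clustering. It describes the printed assumptions, not what the trial will achieve.

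It is also fair to say that the practical consequence is modest, because the printed figure understates the sensitivity that its own inputs imply. The unstated sidedness and the description of a hazard ratio as a likelihood are side points, and the finding does not depend on them.

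**Conclusion.** The point stands as an inconsistency within the power paragraph. On its printed inputs the minimum detectable hazard ratio is about 1.16, with about 93% power at 1.20, against the stated 1.20 at 80%. In events the gap is about 1,410 to 1,440 expected against 945 to 950 needed, a factor of about 1.5. This rests on exponential times, a two-sided test and full 3-month follow-up of each child; one-sided testing widens the gap. The document does not show why the figures differ. An unstated censoring or loss allowance and a smaller sample remain equally open. The absence of a clustering allowance and the conflict between 18 months of recruitment and the shorter trial given elsewhere are separate matters.

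**What to change.** Restate the power paragraph as one consistent set of figures that includes the expected number of events. Either:

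- (a) 1,575 children with complete 3-month follow-up, about 1,410 to 1,440 events, minimum hazard ratio 1.16 at 80% power (about 93% at 1.20); or
- (b) hazard ratio 1.20 at 80% power with about 945 to 950 events, stating the censoring or loss assumption, or the sample size, that yields them.

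If 1.20 was meant to allow for families who stop reporting, (b) is the natural choice and the allowance should be written down. The cost is rewording one paragraph; conduct and analysis do not change.
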